4. CHANGES IN THE PLANNED ANALYSIS OF THE STUDY

5. ENDPOINT(S)

5.1 PRIMARY ENDPOINT(S)

The objective of this study is to determine the safety and tolerability of BI 836880. The primary endpoint is the determination of the maximum tolerated dose (MTD) of BI 836880 based on the number of patients with dose-limiting toxicities (DLTs) during the first treatment cycle. The DLT is defined in section 5.3.1 of the CTP.

The MTD is defined as the highest dose with less than 25% risk of the true DLT probability being above 33%, and may be considered reached if the probability that the true DLT rate is in target interval (16%-33%) is sufficiently large during the MTD evaluation period.

The DLT evaluation period is defined as the time within 3 weeks after first administration of study treatment. The evaluation period will be extended to two more weeks if treatment is delayed due to a drug related AE, For further details, please see CTP section 5.3.1.

Patients, who have not completed first cycle of treatment for other reason than DLT, will be replaced. Patients who were replaced during the MTD evaluation period will not be considered for MTD determination. Those patients that have completed the MTD evaluation period without having been replaced will be referred to as patients evaluable for MTD.

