3.3.4 Removal of patients from therapy or assessments

3.3.4.1 Removal of individual patients

An individual patient is to be withdrawn from trial treatment if:

- The patient withdraws consent, without the need to justify the decision.
- The patient needs to take drugs that interfere with the investigational product or other trial medication (see also [section 4.2.2](#)) or patient require concomitant drugs, which in the opinion of the Investigator may interfere with the investigational drug.

- The patient can no longer be treated with trial medication for other medical reasons (such as surgery, adverse events, other diseases or pregnancy).
- The Investigator may also stop a patient's participation if the patient is no longer able to complete trial visits or trial-required procedures.

A patient can be withdrawn from the trial after discussion between the Investigator and the Sponsor if eligibility criteria are violated and/or the patient fails to comply with the protocol.

All withdrawals will be documented and the reason for withdrawal recorded and discussed, as necessary, in the final report of the trial. As soon as a patient is withdrawn from the trial treatment, the end of treatment visit (EoT) has to be performed if feasible. Every effort should be made to follow-up with patients in case an adverse event is still ongoing at the time of withdrawal. If a patient is withdrawn from the trial due to consent withdrawal, no further visit will be completed.

A patient has to discontinue trial drug administration in case:

- A DLT occurs which does not recover to a degree that allows continuation of treatment (see [section 4.1.4](#) for re-treatment criteria and dose reduction guidelines)
- Progressive disease (PD; except in cases with intra-patient dose escalation, see [section 4.1.3](#)) or start of any new anti-cancer therapy.

Patients who have not completed one cycle of BI 836880 treatment (3 weeks) will be replaced. Patient who terminated treatment due to DLT will not be replaced.

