Patient who discontinue study drug for above mentioned reasons or any other reason prematurely should continue Follow up visits until study end (e.g. progressive disease). Study assessments may be omitted if a patient is willing to return to the pre-defined study visits and may stay on treatment, with the exception of following assessments which are considered mandatory for each Follow up visit: collection of adverse events, patient status, concomitant therapy, safety lab tests including pregnancy test (if applicable), vital signs.

Given the patient's agreement, the patient will undergo the procedures for early treatment discontinuation and follow up as outlined in the FC and [section 6.2.3](#)

For all patients the reason for withdrawal (e.g. adverse events) must be recorded in the Electronic Case Report Form (eCRF). These data will be included in the trial database and reported.

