6.3 PATIENT SETS ANALYSED

Treated set:

This patient set includes all patients enrolled in the trial who were documented to have taken at least one dose of study medication.

Dose finding cohort treated set:

This patient set includes all patients enrolled in dose finding and confirmation of MTD cohort of the trial who were documented to have taken at least one dose of study medication and were evaluable for the MTD determination.

MTD Expansion cohort treated set:

[figure not shown]
This patient set includes all patients enrolled in expansion cohort of the trial who were documented to have taken at least one dose of study medication.

Tumor type expansion treated cohort set (if applicable)

This patient set includes all patients with selected tumor type enrolled in expansion cohort of the trial who were documented to have taken at least one dose of study medication.

PK analysis set (PKS):

This patient set includes all patients with at least one PK sample taken.

[figure not shown]

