7.4 PRIMARY ENDPOINT(S)

The primary endpoint is to assess the MTD based on the number of patients presenting DLTs during the MTD evaluation period. The primary analysis is for the determination of the MTD. The purpose of this analysis is to summarize and document the data that led to the selection of the MTD. Therefore, an overall summary of DLTs (see CTP section 5.3.1 for the definition of DLTs) which occurred during the MTD evaluation period will be provided for each dose cohort from the dose finding cohort treated set. Patients, if any, who did not complete the MTD evaluation period for reasons other than DLT will be excluded from the analysis of the primary endpoint.

A summary of the number of patients with DLTs overall in any course will be also given by initial treatment and displayed in a similar format to the summary of DLTs occurring in the MTD evaluation period.

The analysis of the MTD is based on a Bayesian logistic regression model (BLRM) guided by the escalation with overdose control principle. The MTD is defined as the highest dose for a given schedule that is expected to cause less than 25% risk of the true DLT rate being above or equal to 33% during the MTD evaluation period. Estimation of the MTD during the dose escalation phase of the study will be based upon the estimation of the posterior probability of the incidence of DLT in toxicity categories during the MTD evaluation period for all evaluable patients. The model to be used is specified in CTP section 7.

The posterior probabilities that the toxicity rates of each dose level fall into the categories specified in CTP section 7 will be displayed.

[figure not shown]

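### The MTD population is defined by cycle-1 completion and the recorded reason for leaving, so the literal text can drop an observed DLT from the MTD analysis

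*SAP*

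**What the plan says.** Five places set who counts towards the MTD.

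- SAP 5.1: patients who do not complete the first cycle "for other reason than DLT, will be replaced. Patients who were replaced during the MTD evaluation period will not be considered for MTD determination". It then defines the evaluable group: "Those patients that have completed the MTD evaluation period without having been replaced will be referred to as patients evaluable for MTD".
- SAP 6.3: the dose finding cohort treated set is limited to patients "documented to have taken at least one dose of study medication and were evaluable for the MTD determination".
- SAP 7.4: patients "who did not complete the MTD evaluation period for reasons other than DLT will be excluded from the analysis of the primary endpoint".
- Protocol 3.3.4.1: "Patients who have not completed one cycle of BI 836880 treatment (3 weeks) will be replaced". The one exemption is "Patient who terminated treatment due to DLT will not be replaced".
- Protocol 7.3: the primary analysis is the treated set without the patients who have to be replaced.

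Two further sentences in protocol 3.3.4.1 decide how often the rule can bite. After consent withdrawal there are no more visits: "If a patient is withdrawn from the trial due to consent withdrawal, no further visit will be completed". Patients who only stop the drug stay under observation: "Patient who discontinue study drug for above mentioned reasons or any other reason prematurely should continue Follow up visits until study end".

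Protocol 3.1 treats a patient as resolved for the model update once a DLT has occurred or a full cycle has passed without one.

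On missing data, SAP 6.2 says that patients with important violations that could affect the primary endpoint are excluded. Its table lists missing essential DLT information (code Z3) with no exclusion, and the final decision is left to the report planning meeting before database lock.

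**The concern.** A DLT is an outcome. Once it has been observed in the evaluation period, the patient's contribution to the DLT model is known, whatever happens next. A DLT-free patient who leaves on day 12 is different, because the outcome is unknown and replacement is reasonable. The SAP wording does not separate the two cases.

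Two consequences follow from a literal reading.

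1. A patient has a DLT on day 6 and withdraws consent on day 12. The cycle is not completed, and the recorded reason is not a DLT. The patient is replaced, and an observed primary-endpoint event drops out of the MTD determination.
2. A patient stops early because of a DLT and does not complete the evaluation period. SAP 7.4 and protocol 3.3.4.1 keep this patient. The SAP 5.1 definition of evaluable patients, and through it the SAP 6.3 set, does not, because it has no branch for patients who had a DLT.

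At stake is the numerator of the primary endpoint in cohorts that may be as small as two patients (protocol 3.1). There, one event can decide which doses meet the overdose criterion.

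**Working it through.** **Step 1. Apply the rules to four patients.**

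| Patient | SAP 5.1 replacement | SAP 5.1 evaluable, SAP 6.3 set | SAP 7.4 | Protocol 3.3.4.1 | Protocol 3.1 |
|---|---|---|---|---|---|
| DLT, followed for the full period | not replaced | in | in | not replaced | resolved |
| DLT, stops early because of it | not replaced | out (period not completed) | in | not replaced | resolved |
| DLT, then withdraws consent in cycle 1 | replaced | out | out | replaced, unless read as stopping because of the DLT | resolved |
| No DLT, leaves in cycle 1 | replaced | out | out | replaced | not resolved |

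Rows 2 and 3 are the defect: in row 2 the SAP disagrees with itself, and in row 3 it disagrees with the intent of protocol 3.1.

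**Step 2. The protocol's own illustration.** Protocol Table 10.6:1, after 0/2 at 40 mg:

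- Scenario 4, DLT kept (1/3 at 120 mg): overdose probability at 120 mg is 0.194; stay at 120 mg.
- Scenario 3, DLT patient removed (0/2 at 120 mg): overdose probability at 360 mg is 0.081; 360 mg permitted.

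**Step 3. Recalculation.** Inputs: the model logit p(d) = log(α) + β·log(d/d\*) of protocol 7.1, the three-component prior of Table 7.1:1, overdose meaning a DLT rate of at least 0.33, and a limit of 0.25. The posterior was obtained by numerical integration over a grid. Protocol 7.1 states d\* = 720 mg, but the printed tables reproduce only with d\* = 1250 mg. That is a separate matter, so both are shown.

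Check against the printed figures with d\* = 1250 mg: scenario 3 at 360 mg gives 0.078 (printed 0.081); scenario 4 at 120 mg gives 0.188 (printed 0.194).

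*Small cohort.* After 0/2 at 40 mg, P(overdose at 360 mg):

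| Data at 120 mg | d\* 1250 | d\* 720 |
|---|---|---|
| DLT patient dropped, 0/2 | 0.078 | 0.147 |
| DLT patient counted, 1/3 | 0.530 | 0.620 |
| DLT patient replaced by a DLT-free one, 0/3 | 0.064 | 0.127 |
| The same, DLT also counted, 1/4 | 0.465 | 0.560 |

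Under either reference dose 360 mg is permitted without the DLT and barred with it.

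*Larger cohort (assumed data).* After 0/2, 0/2, 0/3 and 0/6 at 40, 120, 360 and 720 mg:

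| Data at 1000 mg | Overdose at | d\* 1250 | d\* 720 | Permission changes? |
|---|---|---|---|---|
| 0/6 v 1/7 | 1250 mg | 0.112 v 0.278 | 0.054 v 0.218 | only with d\* 1250 |
| 1/6 v 2/7 | 1000 mg | 0.051 v 0.152 | 0.083 v 0.218 | no, permitted both ways |
| 1/6 v 2/7 | 1250 mg | 0.311 v 0.522 | 0.262 v 0.491 | no, barred both ways |

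**Step 4. Direction of bias.** Let p be the true DLT rate, and a and b the probabilities of leaving for another reason with and without a DLT.

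- SAP rule: p(1−a) / [p(1−a) + (1−p)(1−b)]
- Every observed DLT counted: p / [p + (1−p)(1−b)]

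Assume p = 0.25 and b = 0.10; the documents give neither.

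- SAP rule, a = 0.05: 0.2375/0.9125 = 0.260
- SAP rule, a = 0.10: 0.225/0.900 = 0.250
- SAP rule, a = 0.20: 0.200/0.875 = 0.229
- SAP rule, a = 0.40: 0.150/0.825 = 0.182
- Every DLT counted: 0.250/0.925 = 0.270 (0.254 to 0.294 for b from 0.02 to 0.20)

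The SAP rule understates the rate only if a exceeds b. Counting every DLT is closer to the truth only once DLT patients leave about twice as often as others: at a = 0.20 the errors are 0.021 and 0.020.

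**The case against.** The strongest reply is that nobody intended to discard a DLT. Protocol 5.1.1 bases the endpoint on the number of patients with DLTs, protocol 7.3.1 assesses DLTs patient by patient, and protocol 3.1 treats a patient with a DLT as resolved. Protocol 4.1.4 also stops the drug, at least temporarily, at a DLT, so a patient who later withdraws might be recorded as leaving because of it. All of this stands as evidence of intent. It does not settle the text: protocol 3.1 fixes when the model is updated, not who is in the analysis, and no passage says which reason governs.

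The second reply is that the event is rare and would not go unseen. Patients who merely stop the drug remain in follow-up and can still complete the period. DLTs are reported as events of special interest, the DSB decides on all safety data, and the treated-set tables in SAP 7.8 would show the event. This stands, and it limits the consequence.

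Third, the 120 mg decisions are past. The 1000 mg level came with the February 2017 amendment, the SAP is dated June 2017, and the current protocol speaks of two ongoing patients. SAP 7.4 serves to document how the MTD was reached. This also stands.

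A reader might infer that the plan biases the DLT rate downwards. The documents do not support that, because they do not say that leaving is likelier after a DLT; Step 4 shows that the SAP rule can even be the closer of the two.

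A reader might also infer that the Z3 entry lets missing DLT data count as no DLT, with a measurable effect. That goes too far. Protocol 7.5 allows no imputation beyond baseline laboratory values, protocol 5.3.5 counts unproven recovery from grade 4 neutropenia as a DLT, and the DSB charter, which sets the minimum data, is not among the documents. What remains is a conflict of wording within SAP 6.2.

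**Conclusion.** The gap in wording is real, and its severity is minor. Read literally, the plan can remove an observed cycle-1 DLT from the MTD determination, and its definition of evaluable patients omits early DLT stoppers whom other passages keep. Relative to counting every observed DLT, the count can only fall. No bias relative to the true rate is shown.

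Where the case occurs in a small cohort, one lost DLT can change the highest dose the model permits; the 120 mg example does so under both reference doses. In the larger-cohort examples most permissions do not change. The posterior figures rest on the stated prior and on hypothetical data, and the frequency of the case cannot be derived.

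The documents do not show that any dose decision was affected. With escalation probably over, the remaining effect is mainly on the reported MTD analysis. The Z3 conflict is a secondary wording point with no numerical effect claimed.

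**What to change.** 1. In SAP 5.1, 6.3 and 7.4, and in protocol 3.3.4.1 and 7.3, define a patient as evaluable for MTD if the patient had a DLT in the evaluation period, whatever the later reason for leaving, or completed the period without one.
2. State that replacement may add a patient but never removes an observed DLT from the model.
3. Before reporting, check every replaced patient for a DLT in the evaluation period and rerun the model if any is found.
4. Reconcile the SAP 6.2 exclusion sentence, the Z3 entry, the report planning meeting's decision and protocol 7.5, so that a patient with missing DLT status is not silently counted as DLT-free. Exclusion from the MTD determination, unless a DLT was observed or is counted under protocol 5.3.5, is one way to do this.

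The cost is a few sentences and one check of the replaced patients. Counting every DLT while dropping DLT-free leavers can slightly overstate the DLT rate (0.270 v 0.25 under the Step 4 assumptions), which errs on the conservative side.

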4.1.4 Drug assignment and administration of doses for each patient

The study drug will be prepared and handled according to “Instruction for Pharmacists” which will be filed in ISF. Upon notification a patient entered the study; the pharmacy will prepare the study drug in the assigned dosage for administration to the patient.

BI 836880 will be given as 3 weekly intra-venous infusion by authorised site staff in a specialized unit where emergency care can be provided (e.g. intensive care unit available, medical personal trained in advanced live support) according to "Instruction for Pharmacists". The expected infusion time is 90 minutes. In case no relevant infusion reactions are observed, this can be shorten to about 30 minutes but should not be prolonged to more than 6 hours, also in case of technical issues. Appropriate drugs and medical equipment to treat anaphylactic reactions must be immediately available and study personal must be trained to recognize and treat anaphylaxis.

If symptoms of an infusion-related reaction CTCAE grade 2 or higher, but not qualifying as DLT according to [section 5.3.1](#) occur, the infusion should be temporarily stopped. Upon recovery, it should be infused at 50% of the rate at which the reaction occurred. Depending on the time of occurrence and the severity of the reaction, the investigator may consider administering additional supportive medication, e.g. corticosteroids for re-introduction. Infusion rate and premedication for further treatment courses should be adapted according to Investigator decision, but adaption of application scheme need to be agreed with sponsor. An every 2 week application scheme with comparable visit schedule to every 3 week application is optional in case there are no concerns from every 3 week schedule and can only be started with approval by DSB.

Premedication: No premedication will be required for BI 836880 IV infusion. If a patient expressed sign of infusion reaction at any BI 836880 treatment, a premedication will be **considered** for all subsequent treatment infusions (dosage and schedule according investigator's decision) comparable to following scheme:

- Acetaminophen/Paracetamol 650 mg - 1000 mg p.o., or equivalent
- Antihistamine p.o. or i.v., equivalent to Diphenhydramine 50 mg i.v.
- Glucocorticoid i.v., equivalent to prednisolone 100 mg

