6.2.2 Treatment period(s)

A treatment cycle is defined as 3 weeks of duration. If initiation of a subsequent cycle is delayed due to medical reasons, additional visits beyond Day 21 may be necessary and may be performed at investigator's discretion, and should be recorded in the eCRF.

Patients may continue treatment as long as they have clinical benefit (no PD, no toxicities, no new anti-cancer treatment started) and patient is willing to continue.

During cycle 1, 2 and 4 intensive PK-sampling will be conducted and patients have to be observed closely for any adverse events. Therefore patients have to come to the clinic during the first four courses every week to the clinic. Additional visits are needed at day 2 for cycles 1, 2 and 4 and at day 3 for cycle 1. In course 5 and 6 the patient is requested to come to the clinic on day 8 after administration of study drug. From cycle 7 onwards no additional visits, beside day 1 including drug administration, are requested by protocol.

For the 2 ongoing patients, minimum set of procedures is mandatory. This includes safety lab, vital signs including blood pressure, adverse events, and pregnancy test if applicable. However, other assessments as indicated in the flowchart of the protocol or single lab values can be omitted according to investigator's opinion.

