| C1 | Incorrect trial medication taken | To be determined on a case by case basis. Listing will be created and decision will be made at MQRM / BRPM, e.g., incorrect dose taken, dose in course 1 not following dose escalation scheme, overdose, use of expired medication etc. | None |
| C3 | Non-compliance | Study drug not taken according to protocol. To be determined on a case by case basis. Listing will be created and decision will be made at MQRM / BRPM e.g., outside of dosing schedule window, unreasonable drug administration time, etc. | None |
| C5 | Re-treatment criteria not met | Re-treatment criteria was not met according to CTP section 4.1.4 | None |
| D | Concomitant medication | | |
| D2 | Prohibited medication use | Refer to CTP section 4.2.2.1. | None |
| Z | Other | | |
| Z3 | Missing critical safety information in cycle 1 | Essential safety information for the evaluation of DLT is missing | None |

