7.3 TREATMENT COMPLIANCE

Only descriptive statistics are planned for this section of the report.

Compliance will be calculated for subjects having attended the visit. A subject is considered having attended the visit if the indicated visit is captured in the eCRF database. In particular, if a subject attended the visit, but is not treated at the visit, the compliance of this visit is considered as 0%.

Compliance with trial medication will be based on the drug infusion/administered eCRF data and calculated as amount of drug infused/administered divided by the amount of drug to be infused/administered expressed as a percentage, see calculations below.

“Per Visit” Compliance to trial medication will be calculated as follows:

$$\frac{(\text{Amount of drug infused/administered at Visit X(n)})}{(\text{Amount of drug planned to be infused/administered at Visit X(n)})} \times 100$$

Overall Compliance for first treatment cycle of all patients will be calculated as mean of “per visit” compliance at visit Day 1.

Overall Compliance for second treatment cycle onwards (from Day 22 onwards) of all patients will be calculated as mean of “per visit” compliance at each visit. Overall Compliance to trial medication will be calculated as mean of the “per visit” compliance.

The compliance will be based on the total volume infused in mL (eCRF data) compared to total volume prepared (eCRF data).

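### Evaluability for the MTD has no minimum cycle-1 dose, so a substantially under-dosed patient without a DLT can count as a full-dose non-DLT; the exclusion texts in SAP 6.2 conflict and the decision comes too late

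*SAP*

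**What the plan says.** **Who is evaluable.** SAP 5.1: "Those patients that have completed the MTD evaluation period without having been replaced will be referred to as patients evaluable for MTD". It also says: "The DLT evaluation period is defined as the time within 3 weeks after first administration of study treatment" (two more weeks are added if a drug-related event delays treatment). Protocol 3.3.4.1: "Patients who have not completed one cycle of BI 836880 treatment (3 weeks) will be replaced". Protocol 6.2.2: "A treatment cycle is defined as 3 weeks of duration". SAP 6.3 and 7.4 carry this definition into the dose-finding set and the primary analysis. None of these sections states a minimum amount of drug.

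**What happens to dosing errors.** SAP Table 6.2:1, row C1, covers "incorrect dose taken, dose in course 1 not following dose escalation scheme, overdose, use of expired medication etc". Its exclusion column reads None, as it does for C3 (non-compliance) and Z3 (missing DLT information in cycle 1). C1 and C3 are to be judged case by case. The opening paragraph of SAP 6.2, however, excludes patients whose important violations could affect the primary endpoint. It places the exclusion decision at the final report planning meeting before database lock.

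**How a partial infusion can arise.** Protocol 4.1.4 interrupts the infusion for a reaction of grade 2 or higher that is not a DLT. It continues: "Upon recovery, it should be infused at 50% of the rate at which the reaction occurred". The infusion "should not be prolonged to more than 6 hours, also in case of technical issues". Protocol 5.3.1 excepts a controlled, transient grade 3 infusion reaction from the DLT definition.

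**How dose received is measured.** SAP 7.3 first gives a formula with the planned amount as denominator, then says: "The compliance will be based on the total volume infused in mL (eCRF data) compared to total volume prepared (eCRF data".

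**The concern.** The dose-toxicity model takes each patient as a DLT or non-DLT at a dose d. A patient who received a small part of that dose and had no DLT says little about it. If such a patient enters at the assigned dose, the posterior overdose probability falls, and a dose that the overdose rule would close can stay open, or the next one can open. Protocol 3.1 allows escalation on two evaluable patients without a DLT, so one such patient can be half of a cohort's evidence. The shortfall is also not random: it arises in patients who reacted to the infusion.

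**Working it through.** **Inputs.** Model: logit p(d) = log α + β·log(d/d*), with the three-component prior of protocol Table 7.1:1. Overdose: p(d) ≥ 0.33. A dose is allowed if P(overdose) < 0.25 (protocol Table 7.1:2, SAP 7.4). Data: protocol Table 10.6:1. The posterior was integrated numerically on a grid of (log α, log β).

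**Reproducing the plan.** Protocol 7.1 prints d* = 720 mg, but the printed tables reproduce only with d* = 1250 mg. Scenario 7 is 0/2 at 40 mg, 0/2 at 120 mg, 0/3 at 360 mg and 1/3 at 720 mg. P(overdose) at 720 mg is 0.224 with d* = 1250 (printed 0.224), but 0.38 to 0.39 with d* = 720, depending on the grid. Scenario 6 gives 0.024 with d* = 1250 (printed 0.025). The next two checks therefore use d* = 1250.

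**Scenario 7, one of the two non-DLT patients at 720 mg entered at the share received (assumed):**

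| Share of 720 mg | P(overdose) at 720 mg | Under the 0.25 rule |
|---|---|---|
| 100% | 0.224 | open |
| 90% | 0.239 | open |
| 85% | 0.246 | open |
| 82% | 0.251 | at the limit |
| 75% | 0.261 | closed |
| 50% | 0.291 | closed |
| 20% | 0.313 | closed |
| patient removed (1/2) | 0.321 | closed, see below |

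Removal is not the end of the matter. After 1 DLT in 2, protocol 3.1 enrols a third patient at that level. A fully dosed replacement gives 0.224 without a DLT and 0.589 with one.

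**Escalation to 1250 mg after 0/2 at each of 40, 120, 360, 720 and 1000 mg.** P(overdose) at 1250 mg is 0.21. With one of the two patients at 1000 mg entered at 75% it is 0.24, at about 60% it reaches 0.25, and at 20% it is 0.26. With three patients each at 360, 720 and 1000 mg it moves only from 0.17 to 0.20, even at 20%, so the decision does not change.

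**With the printed d* = 720 mg.** Scenario 7 is already closed at full dose. The 1250 mg figure moves from 0.223 to 0.27 at 75%. That path is notional, however: 0/2 at 40, 120 and 360 mg gives 0.37 at 720 mg, so the rule would not have let a two-per-level trial reach it. A reachable case is 120 mg after 0/2 at 40 mg: 1/3 gives 0.210 (open), while 1/2 plus a non-DLT patient at 25% of the dose gives 0.265 (closed). With d* = 1250 that last figure is 0.233, still open.

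**Upper bound on the effect.** Suppose the under-dosed patient has no DLT risk. The chance that a cohort of three shows at most one DLT is then 1 − p² instead of (1−p)³ + 3p(1−p)². At a true rate p = 0.40 this is 0.840 against 0.216 + 0.432 = 0.648.

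**How much dose the infusion rules could cost.** Take a 90-minute infusion with reactions after 15 minutes at full rate and after a further 15 minutes at half rate. Delivered so far: 15/90 + 7.5/90 = 25%. The remaining 67.5 full-rate minutes take 270 minutes at quarter rate, 300 in all. If pauses count towards the 6 hours (an assumption), 90 minutes of pauses gives 25% + (240/4)/90 = 92%, and 120 minutes gives 25% + (210/4)/90 = 83%. Reaching 82% takes about 125 minutes of pauses: 0.57 × 90 × 4 = 205 minutes remain at quarter rate, and 360 − 30 − 205 = 125.

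**The case against.** Several points on the other side stand.

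- **A mechanism for exclusion exists.** A reader might infer that the plan simply keeps every wrongly dosed patient. The general sentence in SAP 6.2 says otherwise, and quality review meetings run periodically during the trial. What remains is a conflict with the None column, and an exclusion decision set after the doses have been chosen.
- **Full-dose entry is not stated.** The model refers only to dose d. The initial-dose wording in protocol 7.3.4 and SAP 7.8.1 belongs to descriptive safety tables. An aborted single infusion might also be read as an uncompleted cycle of treatment, although protocol 6.2.2 defines the cycle by time.
- **Not every shortfall matters.** It is tempting to say that any partial infusion keeps a toxic dose open. The refit does not support that above about 82% in scenario 7, or above about 60% for the 1250 mg step. The worked infusion example reaches such losses only with more than two hours of pauses, and it cannot produce a 20% dose. Larger shortfalls would need an abandoned infusion or a dosing error, and the documents give no frequency for either.
- **The bias is not always towards escalation.** C1 also covers overdose. A non-DLT patient who received more than assigned but is entered at the assigned dose pushes towards caution.
- **Compliance.** A reader might infer that SAP 7.3 cannot detect a preparation error. That holds only for the prepared-volume denominator; the formula above it uses the planned amount. Protocol 4.3 also allows compliance to be verified by pharmacokinetics.
- **Board discretion.** The Data Safety Board reviews all data and may decline to escalate. Protocol 3.1.1 refers to its charter for the minimum data needed, and that charter is not among the documents.

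**Conclusion.** The gap is real and limited. The plan defines evaluability by time, sets no minimum exposure, and contradicts itself on whether a patient with a dosing violation is excluded. For a large shortfall the effect can decide a dose: from 0.224 to between 0.261 and 0.313 at 720 mg in scenario 7 (75% down to 20% received), and from 0.21 to 0.26 for 1250 mg with two patients per level and 20% received. For shortfalls of 15% or less, neither of these two decisions changes.

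This rests on three assumptions: that the assigned dose enters the model, that d* = 1250 mg is what was run, and that the Board does not itself set the patient aside. The effect is therefore possible, not certain. It should be closed before the model is relied on, because the overdose limit protects patients only as well as its inputs allow.

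**What to change.** 1. In SAP 5.1 and 6.3 and protocol 3.3.4.1, count a patient without a DLT as evaluable for MTD only if at least a pre-specified share of the assigned cycle-1 dose was infused. The sponsor sets the share. Otherwise replace the patient under the existing rule. A patient with a DLT in the period stays evaluable.
2. Apply this before each model update for the Data Safety Board, not at the final report planning meeting.
3. Reconcile rows C1, C3 and Z3 of Table 6.2:1 with the exclusion sentence in SAP 6.2.
4. State which dose enters the model. Run one sensitivity model with the mg actually received for all patients, with and without a DLT; recoding only the non-DLT patients would condition on the outcome.
5. In SAP 7.3, settle on one denominator: planned mg.

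The cost is wording plus an occasional replacement patient. Infused volume is already in the eCRF. Infusion management is unchanged.
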